Appendix 1: Participant Baseline Questionnaire (Part-Quest-baseline)

25. Do you expect to be free of your current pain in the future?

- o Yes, in the near future o Yes, in the long term future o No

26. Why did you come to your doctor today? You may choose more than one answer with circles.

- o I want my pain to stop
 o I am worried about the cause of my pain
 o My family made me come
 o I have a personal problem
 o Because of my pain, I can't use my body as I used to

27. Do you take painkillers, and what do you take? (50)

- o Yes, I take _____ .
 If yes, how often do you take them? _____
 o Yes, I take painkillers, but don't remember the name
 o No, I don't take painkillers

28. Do you expect your doctor to give you medication for your pain?

- o Yes, I would like that
 o No

29. If you have a job, how would you generally describe your physical activity in your job? (56) Please choose one.

- o Mostly sedentary work that does not require physical exertion
 o Mostly standing or walking work, which otherwise does not require physical exertion
 o Standing or walking work with some lifting or carrying work
 o Heavy or fast work which is physically strenuous
 o I don't have a job
 o I don't know

In the following last questions mark "x" in yes or no

[figure not shown]
[figure not shown]
	Yes	No
Is your pain radiating to your legs or arms(40)?		
Do you feel anxious(57)?		
Do you think that you have low self-esteem(57)?		
Do you believe in God?		
Is it difficult to fall asleep because of pain(44)?		
Is it difficult to sit during a lesson(44)?		
Does your pain disturb a walk longer than 1 km(44)?		
Does your pain disturb your physical exercise(44)?		
Does your pain disturb your hobbies(44)?		
Do you have pain outside school hours?		
Are you tired during the day(16)?		
Do you feel depressed(44, 57)?		

Does your pain make any of the following activities difficult(40)?	Yes	No
-reaching up to get a book from a high shelf		
-carrying your school bag to school		
-sitting on a school chair for a 45 min. lesson		
-standing in a queue for 10 min		
-sitting up in bed from a lying position		
-bending down to put your socks on		
-standing up from an armchair at home		
-running fast to catch a bus		
-sport activities at school		

Appendix 2: Participant follow-up Questionnaire (Part-Quest-Follow-up)

1. How many consultations have you had with your general practitioner concerning your current musculoskeletal pain condition during the last 3 months(/3 months/6 months at respectively first, second, and third follow-up questionnaires)? _____

[figure not shown]
2. Draw a circle around the stage of your current physical features. Girls draw on the right figure and boys on the left.

3. How tall are you now? _____ cm

4. How much do you weigh now? _____ kg

Below is a drawing of **your** body.

5. Draw on your body, the areas you have had pain or it has hurt, during the past two weeks. If you haven't felt hurt or pain during the past two weeks or currently, please write X here _____

6. Have you felt hurt during the past two weeks leading to not being able to participate in play in the school yard or sparetime activities (ex. football or other sparetime activity)? ? yes _____ no _____

7. Draw a circle around the area of your body, where you have had the **most** problems with pain. You may only draw **one** circle.

[figure not shown]
8. Draw circles around the statements that are true about your pain. You may choose more than one statement.

- it can easily be ignored
- it affects my concentration
- sometimes I have to take pain medication
- sometimes I can't attend school because of the pain

If you are 8 to 11 years old, please answer question 9.

If you are 12 to 19 years old, please *skip* question 9 and answer question 10.

9. These faces show how much something can hurt.

The faces show more and more pain up to this one – it shows very much pain. Circle the face that shows how much you hurt.

10. On a scale of 0 to 10, where 0 is no pain and 10 is the worst possible pain, circle the number that best represents your pain (9).

0 1 2 3 4 5 6 7 8 9 10

Your name _____ Your phone no. _____ Your e-mail _____ 16

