With our primary outcome we aim to capture pain that interferes with their everyday lives and collect the location of pain. The patient characteristics (exposures) are based on results from our systematic review(14), used in other studies (when including references).

The specific wording in the outcomes and throughout the questionnaire has been pilot tested among similar aged kids and adolescents.

Our secondary outcomes highlight the development or potential aggravated psychological and social factors related to musculoskeletal pain at follow-up.

Primary outcome

1) MSK pain influence

Q: Have you experienced pain in the past two weeks that have lead you to not being able to participate in play in the school yard or sparetime activities (ex. football or other sparetime activity)(38)?

If yes, we ask them to draw the area where they have experienced this pain with the following question:

Q: Draw on your body the areas you have had pain during the past two weeks (39).

These two questions will form our primary outcome and will be collected at all endpoints.

Secondary outcomes

1) Problemfilled MSK pain.

*Q: Draw a circle around the area of your body, where you have had the **most** problems with pain. You may only draw **one** circle.*

2) Pain intensity depicted on Faces Pain Scale Revised (FPS-R) or a 10 cm VAS scale for 8-11 and 12-19 year olds respectively (9).

Exposures

3) Self-reported anxiety.

Q: "Do you feel anxious"?

4) Self-reported depression (16).

Q: "Do you feel depressed"?

5) Self-reported low self-esteem (16).

Q: "Do you think that you have low self-esteem"?

6) Duration of troublesome pain episode (40, 41).

Q: "How long does a pain episode usually last"? (see appendix 1 and 2 for the Q in full length).

7) Frequency of troublesome pain episode (10, 42, 43).

Q: "How often do have a pain episode"? (see appendix 1 and 2 for the Q in full length).

8) Nervousness (41).

Q: "How often do you feel nervous"? (see appendix 1 and 2 for the Q in full length).

9) Higher disability index (12, 44).

Q's with yes/no answers:

1. is it difficult to fall asleep because of pain?

2. is it difficult to sit during a lesson?

3. does your pain disturb a walk longer than 1km?

4. does your pain disturb your physical exercise?

5. does your pain disturb your hobbies?

10) Higher HFAQ level (40).

Q: "Does your pain make any of the following activities difficult"?

1. reaching up to get a book from a high shelf

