In relation to our study, all these factors have an interest as to whether they present as prognostic factors in MSK pain at follow-up. We questioned whether it would be ethical to ask the question “Do you feel Danish?”, why we conducted an intern survey among a group of seven immigrants and one descendant, representing five countries, from Europe and the Middle East. Among the immigrants, only one felt offended by this question. The rest did not, but two out of these said they would have felt offended, if they were born in Denmark. The descendant was not offended by the question. We decided to keep this question as part of our questionnaire and keep it applicable for all participants including the ethnic Danes, because we can't presuppose this patient groups' answer to this question. Hence the answer is a potential prognostic factor.

The questionnaires will be pilot tested among target participants; Part-Quest among 8-19-year-olds with MSK pain and the Pare-Quest among parents to children with MSK pain.

Translation of questionnaires

Our questionnaires will be cross-cultural adaptive for participants with poor Danish language skills, insufficient to comprehend the original Danish questionnaires. In the process of translation and validation, we will translate our questionnaires both linguistically and culturally. Our three questionnaires and our bulletin will be translated from English to Danish, which is the mother tongue of the majority of our prospective participants.

The Part-Quest, Pare-Quest, and The Faces Pain Scale Revised (FPS-R) will be translated into Danish, following the general methodology of translation, back-translation, and verification (46):

1. English to Danish. Translation by a pool of 5-7 researchers fluent in English and Danish, with the latter as their mother tongue.
2. The Danish version will be read by 3-4 teachers, nurses, or physicians who are all familiar with young children's use of language, to ensure suitability for children 8-11 years of age.

3. The Danish version will be back-translated into English by a bilingual person who does not know anything about the questionnaires and has not seen the original version. The original and the back-translated versions will be compared and needed adjustments will be made.
4. The Danish version will be pilot-tested with 2-3 children 8-11 years of age.

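### The printed questionnaire items do not ask the primary outcome as the protocol defines it: item 6 drops the word pain, and the body drawing is no longer tied to a yes answer.

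*Protocol*

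**What the plan says.** The Protocol, under Outcomes – Primary outcome, builds the primary outcome from two linked questions. The first is "Have you experienced pain in the past two weeks that have lead you to not being able to participate in play", extended to spare-time activities. The second is a body drawing that depends on the first: "If yes, we ask them to draw the area where they have experienced this pain with the following question". The section then states "These two questions will form our primary outcome and will be collected at all endpoints".

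The participant forms differ. Item 6 in Appendix 2 (follow-up) reads "Have you felt hurt during the past two weeks leading to not being able to participate in play in the school yard", and item 6 in Appendix 1 (baseline) uses the same words. The drawing is item 5, placed before item 6: "Draw on your body, the areas you have had pain or it has hurt, during the past two weeks". A child without pain can opt out: "If you haven't felt hurt or pain during the past two weeks or currently, please write X here". Nothing on either form links the drawn areas to the answer on item 6.

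On testing, the Outcomes section says "The specific wording in the outcomes and throughout the questionnaire has been pilot tested among similar aged kids and adolescents", while the Questionnaires section describes pilot testing of the questionnaires as still to come. On language, the section on translation says "Our three questionnaires and our bulletin will be translated from English to Danish". The Farsi and Arabic versions are then made from the Danish.

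**The concern.** The instrument as printed does not put the defined question. There are two departures.

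- **The trigger word.** The definition asks about pain. Item 6 asks about feeling hurt, which in English is the looser term.
- **The link.** In the definition, the drawing shows where the activity-limiting pain was. On the form it shows any pain in the past two weeks, limiting or not.

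Together these leave a gap. All participants enter with musculoskeletal pain, so some who are no longer limited by it may still mark an area in item 5. If such a child says yes to item 6 for a reason other than that pain, both parts of the outcome appear to be met.

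This would matter most if it were related to an exposure. Anxiety, depression and low self-esteem are listed as exposures in the Outcomes section, and the parent form asks about solitary play and bullying. A loose reading of item 6 that is commoner in distressed children would move those associations away from their true value.

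**Working it through.** The plan gives no figure on this point to reproduce, and the sample size does not depend on the wording. The check is a comparison of text, followed by an illustration of size.

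**Comparison of the definition and the forms**

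| Element | Primary outcome section | Appendices 1 and 2 |
|---|---|---|
| Trigger | has experienced pain | has felt hurt (item 6; no mention of pain) |
| Consequence | could not take part in play or spare-time activities | same |
| Order | interference question, then drawing | drawing (item 5), then interference question (item 6) |
| Condition on drawing | only after a yes | none, except the X for no pain or hurt |
| What the drawing covers | introduced as the location of the limiting pain | any area of pain or hurt in two weeks |

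**Who could be misclassified.** Take the natural two-part reading: a case needs a yes on item 6 and a drawn area.

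1. No drawn area, yes on item 6: not a case, whatever the child meant by the yes.
2. Drawn area, limiting pain, yes: a true case.
3. Drawn area, non-limiting pain, yes for another reason: counted as a case on the printed form, but not under the definition.

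Only group 3 is at issue.

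**Illustration of size.** Let p be the true proportion of cases, d the share of non-cases who still draw an area, and f the share of those who say yes for another reason. The observed proportion is p + (1 − p)·d·f. The Sample-size section assumes that 50% continue to have pain at the primary follow-up. I use p = 0.5, although the interference outcome could be rarer. The values of d and f are assumptions; the documents give neither. With no true association and p = 0.5, the apparent odds ratio is

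OR = [(1 + d·f₁)/(1 − d·f₁)] / [(1 + d·f₀)/(1 − d·f₀)],

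where f₁ applies to distressed children and f₀ to the others.

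| f₁ / f₀ | d = 0 | d = 0.5 | d = 1 |
|---|---|---|---|
| 5% / 1% | 1.00 | 1.04 | 1.08 |
| 10% / 2% | 1.00 | 1.08 | 1.17 |
| 15% / 3% | 1.00 | 1.13 | 1.27 |

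For the middle cell, (1.05/0.95)/(1.01/0.99) = 1.105/1.020 = 1.08. At p = 0.40, the 10% / 2% row gives 1.10 for d = 0.5 (0.430 versus 0.406) and 1.22 for d = 1 (0.460 versus 0.412). If every child reads item 6 as physical pain, f₁ = f₀ = 0 and the odds ratio is 1.00 throughout.

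**The case against.** The strongest reply is that, in context, item 6 plainly means physical pain. Item 5 pairs hurt with pain immediately before it. Item 7 asks for the area with the most pain problems, item 8 is about the child's pain, and the faces scale in item 9 uses hurt as its word for pain intensity. The children were recruited because they told a GP about musculoskeletal pain. This stands, and it may reduce the effect to nothing.

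A reader might infer that children with hurt feelings and no pain would be counted as cases. The documents do not support that. The outcome also needs a drawn area, and a child who writes X or draws nothing does not meet it on the two-part reading.

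A reader might also infer that the ambiguity passes into every language version. That cannot be determined. The double meaning is a feature of the English, and the Danish form is not shown. The translation plan includes several bilingual translators, reading by people familiar with young children's language, back-translation and a pilot with children aged 8–11. On the other hand, the back-translation is compared with the English form, so it would not necessarily reveal that the form departs from the Primary outcome section.

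Finally, the pilot-testing sentence covers the questionnaire as well as the outcomes, so it does not show that item 6 was untested. It leaves open which of the two wordings was tested.

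None of these replies restores the missing link between the yes and the drawing.

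**Conclusion.** The mismatch is real, concerns the primary outcome and appears in both participant forms: the defined question is not the one printed, and the conditional drawing has become unconditional. What follows is narrow. A child with non-limiting pain who answers yes for another reason could be counted as a case, and if that is commoner among distressed children, associations with anxiety, depression and self-esteem could be biased.

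The documents demonstrate no such bias. Under the assumed rates, apparent odds ratios at p = 0.5 run from 1.00 to 1.27. The upper end needs every non-case to draw an area and a false-yes rate of 15% in distressed children. The conclusion also assumes that a case requires both a yes and a drawn area, which is the natural reading of the Primary outcome section. It would be too strong to say that the forms produce a spurious psychological prognostic factor. Severity is moderate to minor.

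**What to change.** 1. In item 6 of Appendices 1 and 2, use the Primary outcome section's wording about having experienced pain.
2. Tie the drawn area to a yes on that item, as the Primary outcome section states. One way is to keep item 5 as a general drawing, so that sites of non-limiting pain are not lost, and add after item 6 an instruction to those answering yes to mark where the limiting pain was.
3. State which wording was or will be piloted, and confirm that the same version is the source for translation.
4. If forms are already in use, check how item 6 reads in Danish, Farsi and Arabic, and record the form version as a variable so that results can be compared across versions.

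The cost is one changed sentence and one added instruction on each of two forms. The burden on participants is negligible and the sample size is unaffected. If the forms have already been translated, the changed lines need translating and checking again.

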Appendix 1: Participant Baseline Questionnaire (Part-Quest-baseline)

1. Is this your first consultation with your general practitioner concerning your current musculoskeletal pain condition? Mark one answer.

Yes No, this is consultation number _____ with my current musculoskeletal pain condition

[figure not shown]
2. Draw a circle around the stage of your current physical features. Girls draw on the right figure and boys on the left.

3. How tall are you? _____ cm

4. How much do you weigh? _____ kg

Below is a drawing of **your** body.

5. Draw on your body the areas you have had pain or it has hurt, during the past two weeks. If you haven't felt hurt or pain during the past two weeks or currently, please write X here _____ (50)

6. Have you felt hurt during the past two weeks leading to not being able to participate in play in the school yard or sparetime activities (ex. football or other sparetime activity)? yes _____ no _____

7. Draw a circle around the area of your body, where you have had the **most** problems with pain. You may only draw **one** circle.

8. Mark the statements below, that are true about your pain. You may mark more than one.

[figure not shown]
- it can easily be ignored
- it affects my concentration
- sometimes I have to take pain medication
- sometimes I can't attend school because of the pain.

If you are 8 to 11 years old, please answer question 9.

If you are 12 to 19 years old, please *skip* question 9 and answer question 10.

9. These faces show how much something can hurt.

This face shows no pain.

The faces show more and more pain up to this one – it shows very much pain. Circle the face that shows how much you hurt (46).

10. On a scale of 0 to 10, where 0 is no pain and 10 is the worst possible pain, circle the number that best represents your pain (9).

0 1 2 3 4 5 6 7 8 9 10

Your name _____ Your phone no. _____ Your e-mail _____ 13

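### The faces pain item for 8-11-year-olds labels the no-pain face at baseline but, as printed, not at follow-up

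*Protocol*

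**What the plan says.** The Outcomes section lists as secondary outcome 2: "Pain intensity depicted on Faces Pain Scale Revised (FPS-R) or a 10 cm VAS scale for 8-11 and 12-19 year olds respectively".

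In Appendix 1, item 9 gives the youngest band an opening line, then "This face shows no pain", then the upper label and the instruction to circle a face.

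In Appendix 2, item 9 opens with the same line, "These faces show how much something can hurt", and the next printed text is "The faces show more and more pain up to this one – it shows very much pain. Circle the face that shows how much you hurt". No sentence labelling the no-pain face stands between them.

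Item 10, for ages 12-19, carries the same lower label on both forms: "On a scale of 0 to 10, where 0 is no pain and 10 is the worst possible pain".

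The follow-up form sends children to the faces by age only: "If you are 8 to 11 years old, please answer question 9". Absence of pain can be recorded elsewhere on that form, in item 5: "If you haven't felt hurt or pain during the past two weeks or currently, please write X here".

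**The concern.** A repeated measurement should be asked in the same way each time. Here one line of the instruction changes between baseline and follow-up, in one age band only.

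The change falls where the lower label has most work to do. At recruitment every participant must have self-reported musculoskeletal pain, so few should need the no-pain face. At the primary follow-up the Sample-size section assumes that 50% still have pain, so about half are expected not to. A pain-free child of 8 to 11 is still told to circle a face, has been told that the faces show how much something hurts, and finds no face labelled as no hurt. Follow-up forms also arrive by e-mail, whereas the baseline form is handed out on paper at the clinic, so the printed instruction matters more at follow-up.

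If some of these children circle a higher face than they would with the label, intensity at ages 8-11 is shifted upward at follow-up only. Because form and time point coincide completely, the data could not separate such a shift from a real course of pain.

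**Working it through.** The protocol states no figure for this item, so the check is a comparison of texts.

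**Item 9 (ages 8-11), part by part**

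| Part of the instruction | Appendix 1 (baseline) | Appendix 2 (follow-up) |
|---|---|---|
| Opening line | present | present, same words |
| Label for the no-pain face | present: "This face shows no pain" | not printed |
| Upper label | present: "The faces show more and more pain up to this one – it shows very much pain" | present, same words |
| Instruction to circle a face | present | present, same words |

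**Item 10 (ages 12-19):** zero is labelled as no pain on both forms.

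**Routing at follow-up:** by age alone. No skip is printed for a child who marked no pain in item 5, and the protocol does not say that such a mark sets or overrides the item 9 score.

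**Which results could be touched:** only secondary outcome 2 at ages 8-11. The primary outcome rests on items 5 and 6, which do not involve the faces. Children of 8-11 at a given visit all receive the same wording, so comparisons among them share it.

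**How many children are in the relevant position.** The documents give no age distribution. Assume an even spread over the 12 age years from 8 to 19, of which 8-11 make up 4.

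- Participants at follow-up: 480, the protocol's number before it adds 5% for loss to reach 504.
- Aged 8-11: 480 × 4/12 = 160.
- Without pain, at the protocol's 50%: 160 × 0.50 = 80.

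Some children will turn 12 and move to item 10 before a later follow-up, which lowers this number.

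**Size of a shift.** Let q be the share of pain-free children who circle the next face up because zero is unlabelled, and d the score step between neighbouring faces. The shift in the 8-11 follow-up mean is 0.50 × q × d. Neither q nor d is in the documents. Purely to show the scale, assume d = 2 on a 0-10 scoring and q between 10% and 30%:

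- Children affected: 80 × 0.10 = 8, to 80 × 0.30 = 24.
- Mean shift: 0.50 × 0.10 × 2 = 0.1, to 0.50 × 0.30 × 2 = 0.3 points.

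The range for q has no source, so this is an illustration and not an estimate.

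**The case against.** The strongest objection is that the line may be missing only from the text as read from the PDF. The faces themselves are not shown on either form, the sentence is short and could be a caption to the first face, and the layout of the appendices is disturbed elsewhere. This cannot be excluded, and it makes the point conditional on the original form. It does not remove the point: the same sentence was read as ordinary text in Appendix 1, and the two forms were worded separately in other items. Item 8 asks for marks at baseline and circles at follow-up, and the pain-frequency item has an extra option at follow-up. A real omission is plausible.

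A reader might infer that the zero of the scale is undefined at follow-up. The documents do not support that. The outcome is a named scale, the text still describes faces of increasing pain up to a maximum, so the order and low end are implied, and participants were given the labelled version at baseline. Item 5 also identifies children without pain.

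A reader might infer that improvement from baseline is understated. The protocol states no analysis of change in intensity; its objective is the association of baseline factors with pain at follow-up. Nor can a difference between the age bands be pinned on this sentence, since the bands use different instruments by design.

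A reader might see a contradiction with the statement under Statistical methods that identical questionnaires are used. That statement concerns all patients, not all time points, and is not clearly contradicted.

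Finally, the Danish, Farsi and Arabic forms are not in the documents, so it cannot be said that they lack the label. The protocol plans back-translation, comparison and a small pilot for the Danish version, and the use of existing Persian and Arabic versions of the scale. These steps may catch the gap, but none is described as a comparison of the follow-up form with the baseline form.

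**Conclusion.** The point holds in a limited form and is minor. As printed, a named secondary outcome is asked of 8-11-year-olds with a labelled no-pain face at baseline and an unlabelled one at follow-up, while the older band keeps its labelled zero throughout. The direction of any effect would be upward at follow-up in this band, but that it occurs is a possibility and not a demonstrated bias, and its size cannot be derived from the documents. Under an even age spread and the protocol's 50% assumption, about 80 pain-free children would face the unlabelled item at the primary follow-up. The primary outcome is untouched, and comparisons among 8-11-year-olds at one visit share the same wording. All of this rests on the sentence being absent from the original follow-up form, which needs to be confirmed.

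**What to change.** Check item 9 of the original follow-up form. If the sentence is absent, restore "This face shows no pain" with its pointer to the first face, between the opening line and the upper label, so that Appendix 2 matches Appendix 1. Check that the Danish, Farsi and Arabic follow-up versions carry the same label.

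If follow-up forms have already gone out without it, record which version each child received and note this when reporting follow-up intensity at ages 8-11.

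The cost is one line in the form, plus a check of the translations. It needs no further participants or procedures and adds no burden for the children.
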